12.5. Statistical Data Management

F&P may consult an external statistician to assist with the analysis of the data collected from participants.

13. Safety and Reporting

13.2. Non-significant Risk

F&P has assessed the potential risk of the investigational product when used as part of this clinical investigation, and believe it to be a non-significant risk. This clinical investigation will attempt to recruit individuals who have already been prescribed and are currently undergoing in-home PAP therapy as treatment for a respiratory condition.

[REDACTED]

13.3. Adverse Events

An AE is any adverse change from the baseline condition of a participant, and is considered as any unfavorable and unintended symptom or disease that occurs over the course of the clinical investigation, whether related or unrelated to use of the investigational product or PAP therapy. All clinically significant AEs that occur during the clinical investigation that were not present prior to commencement of the clinical investigation, will be recorded in the CRF of the affected participant, and followed up by the PI until resolution or stabilization of the condition among participants occurs in accordance with GCP. The collection of AE data will commence once the participant is fitted with the investigational product at Visit [REDACTED] and up to 24 hours after the investigational product is returned at [REDACTED]

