1.1. List of Terms

Abbreviation	Definition
AE	Adverse event Any untoward medical occurrence, unintended disease, or injury, or clinical signs, including abnormal laboratory findings, among participants enrolled in the clinical investigation, regardless of if they arise due to use of the investigational product. See also: SAE
AHI	Apnea-Hypopnea Index Measure of sleep apnea severity calculated from the number of apneic and hypopneic episodes combined per hour of sleep which last more than 10 seconds and are associated with a decrease in blood oxygenation. ¹
APAP	Auto-titrating positive airway pressure Mode of non-invasive ventilation during which a low set pressure is supplied to the airway, unless an obstruction is detected, in which case this ramps up to a higher pressure. ¹
BPAP	Bi-level positive airway pressure Mode of non-invasive ventilation during which two distinct pressures, one at inhalation and the other at exhalation, are supplied to the airway. ¹
[REDACTED]	
CIA	Clinical Investigation Administration Physical and electronic folder which corresponds to a unique identification number created by F&P for clinical investigations, to house relevant contracts, documentation, and memos.
CIP	Clinical Investigation Plan Document that states the proposed rationale, objectives, design, methodology, monitoring, organization, conduct, statistical considerations, analysis, and record-keeping for an intended clinical investigation.
CMD	Clinical Master Data A compilation of up-to-date clinical data related to a therapy and associated medical procedures which is generated using a comprehensive search protocol and appraisal strategy.
CPAP	Continuous positive airway pressure Mode of non-invasive ventilation during which a fixed pressure with constant flow is supplied to the airway during inhalation and exhalation.
CRF	Case Report Form Deidentified document used by research personnel carrying out a clinical investigation to record source information relating to a participant, including data which is collected and procedures that are followed.

CTA	Clinical Trial Agreement Formal contract between the sponsor organization and investigation site outlining the roles and responsibilities for both parties conducting the clinical investigation.
DHF	Design History File Compilation of documentation that describes the design and development history of the investigational product.

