9.7. Enrolment Eligibility

Below are the inclusion criteria for enrolment in the clinical investigation:

- Persons who are ≥ 22 years of age
- Persons who weigh ≥ 66 pounds
- Persons who have been prescribed PAP therapy by a physician
- Persons who are existing nasal pillows mask users with ≥ 3 months of use prior to enrolment in the clinical trial
- Persons who are compliant with PAP therapy for ≥ 4 hours per night for $\geq 70\%$ of nights for a 14-day period within 30 days prior to enrolment in the clinical trial
- Persons who are fluent in spoken and written English
- Persons who possess the capacity to provide informed consent

Below are the exclusion criteria for enrolment in the clinical investigation:

- Persons who are intolerant to PAP therapy
- Persons who possess, or suffer from, anatomical or physiological conditions which make PAP therapy inappropriate
- Persons who are required to use PAP therapy for >12 hours per day or for extensive periods, not including sleep or naps
- Persons who are trying to get pregnant, are pregnant, or think they may be pregnant
- Persons who have an IPAP pressure of >25 cmH₂O if on BPAP
- Persons who use a PAP therapy device for the delivery of medicines, except supplemental oxygen
- Persons who use a PAP therapy device that does not possess data recording capabilities to capture AHI and a numerical indicator of leak that is accessible to the investigation site

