10.13. Follow-up Plan

[figure not shown]
All participants are free to receive standard care from their medical provider or healthcare professional throughout and after the completion of the clinical investigation. Participants will be followed up with throughout the duration of their enrolment in the clinical investigation, defined as the date informed consent is completed up to the date the participant either attends their final appointment at the investigation site or is formally withdrawn. [REDACTED]

[REDACTED], participants will be obliged to report any AEs or SAEs for 24 hours after either their last use of the investigational product or their last contact with the investigation site for the purposes of the clinical investigation, regardless of whether they have completed the clinical investigation or have been withdrawn. There will be no active follow-up during this period, but participants will be informed of the requirement to report any AEs appropriately. This 24-hour period is deemed acceptable because once the investigational product is no longer in contact with the participant, there is no mechanism for new AEs

related to the intervention to occur. Moreover, as the investigational product does not interact with internal systems or structures of the body and there are no metabolization risks or anticipated residual impacts on the individual. The most obvious risks associated with PAP therapy mask use which is incompatible with the user, such as reddening, itching, or swelling of the skin, generally appear quickly upon initial application of the medical device, but will subside when use is discontinued.

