10.14. Foreseeable Complications

From the Manufacturer and User Facility Device Experience database, the common reported injuries from PAP therapy and associated interface use are pressure sores, leading to cuts, rashes, and skin abrasions and breakdown. Allergic reaction to materials in the interface can occur. Common complaints are discomfort and soreness on the areas of contact with the interface. Participants on the clinical investigation are informed that they can switch back to their usual mask if required. In instances of malfunction or damage, the investigational product and its components may be replaced, with this recorded in the CRF. In the event that participants require additional healthcare after they have been involved in this clinical investigation, and this medical attention is necessary because of the participant partook in the clinical investigation or differs from that normally expected as part of their usual healthcare or follow-up, the PI will be responsible for ensuring availability and access to appropriate healthcare. The investigation site will provide evidence of an emergency plan of action to F&P for any participants who required this additional healthcare.

11. Clinical Investigation Documentation

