13.5. Expected Side Effects

Throughout the clinical investigation, participants may experience a poor night sleep with the investigational product as it will be different to the usual mask they use. These are disclosed in the ICF issued to participants and will be documented as expected side effects in the CRF, but not as AEs. Participants will be informed that these side effects are expected as a consequence of receiving PAP therapy, particularly when you initially begin use, and may subside over time with continued adherence to treatment. They will also be advised that if these side effects are unduly intrusive to their daily life or prevent them from using PAP therapy to manage the respiratory condition for which it was prescribed, to consult the PI or contact the investigation site. Alternatively, participants can switch back to using their usual mask for PAP therapy.

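### Section 13.3 requires recording of fewer adverse events than the plan's own definition covers: "clinically significant" has no visible criterion, and the treatment of worsening is ambiguous

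*Combined protocol and SAP*

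**What the plan says.** Two definitions of an AE appear, both broad. The list of terms (1.1) begins "Any untoward medical occurrence, unintended disease, or injury, or clinical signs". Section 13.3 says "An AE is any adverse change from the baseline condition of a participant", whether or not it is related to the mask or to PAP therapy. Neither sets a severity threshold.

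The recording rule is the next sentence of 13.3. What goes into the CRF and is followed up by the investigator is "All clinically significant AEs that occur during the clinical investigation that were not present prior to commencement of the clinical investigation".

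Four other places bear on this:

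- Section 10.14, on foreseeable complications, lists pressure sores, rashes and abrasions, and adds: "Common complaints are discomfort and soreness on the areas of contact with the interface".
- Section 10.13 describes the most obvious risks as those "such as reddening, itching, or swelling of the skin, generally appear quickly upon initial application of the medical device".
- Section 9.7 enrols "Persons who are existing nasal pillows mask users with ≥ 3 months of use prior to enrolment in the clinical trial".
- Section 13.5 deals with expected side effects, which "will be documented as expected side effects in the CRF, but not as AEs". The only one it visibly names is a poor night's sleep.

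**The concern.** A recording rule should capture whatever the definition calls an AE. Here the rule adds two conditions that the definition lacks: clinical significance and absence before the study began. An event can meet the definition and still carry no duty to record it.

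Section 12.1 describes a confirmatory design, meant to show that the mask is safe and effective before global release and to support clearance applications. Section 10.2 says there is no control group and no blinding. Whoever decides that an event is not clinically significant knows which mask was worn, and no concurrent arm would reveal under-recording. Any loss lowers the AE count, which favours the mask. Serious events have their own definition in 13.4, so non-serious local harms are a large part of what a study of 40 to 45 people can show about safety.

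**Working it through.** The plan states no AE rate and no visible safety threshold, so there is no figure to reproduce. The check compares the texts.

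**1. Clinical significance.** The definition covers any adverse change; the rule covers only the clinically significant ones. The visible text gives no criterion, names no judge, and nowhere requires the remaining AEs to be recorded. No reading of this condition makes the rule match the definition.

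**2. Not present before.** Two readings are open.
- If the phrase applies to the underlying condition, a sore that existed at entry and worsens on the new mask is outside the rule, although it is an adverse change from baseline.
- If it applies to the AE itself, the worsening is inside the rule. An AE is a change from baseline, and a change cannot already be present at baseline.

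The text does not choose between them, so site staff could apply it either way.

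**3. Which harms are affected.** Sections 10.13 and 10.14 name soreness, discomfort, reddening, itching and swelling. Many such events could be mild, so the first condition bears on them directly. The second matters only if participants have complaints at entry. That is plausible after at least three months on nasal pillows, but the documents do not establish it.

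**4. Other routes.** Section 13.5 keeps expected side effects in the CRF. Section 12.1 mentions participant questionnaires. Section 11.2 records reasons for withdrawal and discontinuation. Section 10.13 obliges participants to report any AE in the 24 hours after last use or last contact. Each may catch some events, but none visibly restores a full AE count.

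**5. Scale, purely as illustration.** Let n be the number of participants (40 to 45, section 9.6), p the true proportion with any adverse skin or contact change, and f the share removed by the two conditions. Both p and f are assumptions; the documents give neither. The expected number of participants with a recorded event is n × p × (1 − f):

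| p | n | f = 0 | f = 0.5 | f = 0.8 |
|---|---|---|---|---|
| 5% | 40 | 2.0 | 1.0 | 0.4 |
| 5% | 45 | 2.25 | 1.1 | 0.45 |
| 10% | 40 | 4.0 | 2.0 | 0.8 |
| 10% | 45 | 4.5 | 2.25 | 0.9 |
| 30% | 40 | 12.0 | 6.0 | 2.4 |
| 30% | 45 | 13.5 | 6.75 | 2.7 |

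The chance of recording no event at all is (1 − p(1 − f))^n. With p = 10% and f = 0.8 it is 0.98^40 = 45% or 0.98^45 = 40%. With full recording it is 0.90^40 = 1.5% or 0.90^45 = 0.9%. In a study this small an AE count can depend heavily on the recording rule. The table says nothing about what p and f are here.

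**The case against.** Five points can be made for the plan.

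- **The rule is a minimum.** It says what must be recorded and forbids nothing more. A reader might infer that milder events go uncounted and are lost for good. The documents do not support that, because staff may record more and the other routes may hold some of the information. What stands is that these events need not be recorded as AEs.
- **Worsening may already be covered.** A reader might infer that worsening of an existing complaint is definitely excluded. The change-from-baseline definition allows the opposite reading, so only ambiguity is shown. Section 10.13 also says skin reactions tend to appear soon after first application. That points to new events at fitting, which would satisfy the second condition.
- **Text is redacted.** Part of 13.3, the CRF content, the visit procedures and the acceptance criteria are blacked out or absent. A criterion, a named judge or a symptom check at fitting may be there. This limits the claim to the visible text, but the two visible sentences of 13.3 still differ in scope.
- **No visible conclusion changes.** A reader might infer that zero recorded events would be presented as an AE rate below 7.2% (1 − 0.05^(1/40)) or 6.4% (1 − 0.05^(1/45)). The plan makes no such inference in its visible text. The tests in 12.1 are one-proportion tests of product requirements, and no pass or fail result is shown to depend on the AE count.
- **Full recording meets 13.5.** Poor sleep could satisfy the AE definition, yet 13.5 says it is not recorded as an AE. This is correct, and any change to 13.3 has to deal with it.

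**Conclusion.** The point holds in a limited form. In the visible text of 13.3, the recording rule is narrower than the definition beside it. The clinical-significance condition is the firm part: without a criterion or a named judge, it leaves milder expected harms with no duty to record them as AEs. The wording on prior presence is ambiguous about worsening and should be settled.

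The consequence is a possible under-count of AEs, in the mask's favour. Its size is unknown, because it depends on how often mild or worsened events occur, how staff apply the conditions, how much the other routes recover, and what the redacted text contains. The conclusion itself rests on the two sentences of 13.3 and not on any assumed rate. It is worth correcting before enrolment, since the study is meant to support a safety claim and the correction is cheap.

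**What to change.** In section 13.3:

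- Require CRF entry of every event that meets the AE definition.
- State that worsening in severity or frequency of a condition present before fitting counts as an AE.
- Record severity and relationship to the mask for each event.
- Keep clinical significance only as a flag on the CRF, with a stated criterion and a named role that applies it.
- Note symptoms present at first fitting, if the redacted visit procedures do not already do so, so that worsening can be judged.
- Report counts for all AEs and for flagged AEs.

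Reconcile this with 13.5 by listing which expected side effects fall under that section, such as poor sleep, and tabulating them separately from AEs.

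The cost is wording in two sections and a few CRF fields. No visit, sample size or treatment changes. The downside is more minor entries and a higher, less favourable AE count.

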13.4. Serious Adverse Events and Reporting

SAEs are considered any harmful outcomes experienced by participants which result in any of the following, regardless of their relationship to use of the investigational product or PAP therapy:

- Death
- Life-threatening AE
- Unplanned in-patient hospitalization or prolongation of existing hospitalization
- Persistent or significant disability or incapacity
- Permanent irreversible impairment of a body function or damage to a body structure
- Congenital abnormality or birth defect

13.5. Expected Side Effects

Throughout the clinical investigation, participants may experience a poor night sleep with the investigational product as it will be different to the usual mask they use. These are disclosed in the ICF issued to participants and will be documented as expected side effects in the CRF, but not as AEs. Participants will be informed that these side effects are expected as a consequence of receiving PAP therapy, particularly when you initially begin use, and may subside over time with continued adherence to treatment. They will also be advised that if these side effects are unduly intrusive to their daily life or prevent them from using PAP therapy to manage the respiratory condition for which it was prescribed, to consult the PI or contact the investigation site. Alternatively, participants can switch back to using their usual mask for PAP therapy.

13.6. Early Termination

The clinical investigation may be discontinued at any time on advice or instruction from the PI, or on the basis of new information regarding the safety or efficacy of the investigational product arising. Moreover, the clinical investigation may be terminated if progress is unsatisfactory.

The following is required if the appropriate party decides to terminate the clinical investigation:

- If the PI terminates or suspends the clinical investigation without prior agreement with F&P, the PI should inform the institution, when and where required by the applicable regulatory requirements. The PI and institution should promptly inform F&P and the IRB, and provide a detailed written explanation of the termination or suspension
- If F&P terminates or suspends the clinical investigation, the PI should promptly inform the institution, when and where required by the applicable regulatory requirements. The PI and institution should promptly inform the IRB, and provide a detailed written explanation of the termination or suspension
- If the IRB terminates or suspends its approval or favorable opinion of the clinical investigation, the PI should inform the institution, when and where required by the applicable regulatory requirements. The PI and institution should promptly inform F&P, and provide a detailed written explanation of the termination or suspension.

14. Publication Policy

14.1. Presenting Results

[REDACTED]

15. Approval

16.1. Internal References

[REDACTED]	[REDACTED]

